Microdialysis placement: Four microdialysis fibers (Bioanalytical Systems) with a membrane length of 10mm and a 20-kDa cutoff will be inserted on the dorsal side of the forearm. Microdialysis fibers will be placed by [name] or doctoral student trained by [name]. Under sterile conditions the fibers are placed in the intradermal space with a 23-gauge needle used as a guide cannula. Ice is used on the site locally to numb the skin, reduce blood flow, and minimize release of vasoactive substances. The entrance and exit site on the skin are separated by at least 2 cm. The guide cannula is inserted horizontally in the dermis and the microdialysis fiber is fed through the guide cannula. The needle is removed, and the fiber left in place at a depth of \approx 2-5 mm. After placement, the fiber is perfused with lactated Ringers at a rate of 2 μ l/min using a syringe pump (Bioanalytical Systems, Inc.) for 90 minutes. This recovery period (after fiber insertion) is required to allow local skin blood flow (SkBF) to return to baseline before data measurements can be made. During the recovery period, the subject will be instrumented for the measurement of heart rate (ECG) and blood pressure.

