ET-1 receptor antagonists: ET-A and ET-B receptor antagonists (BQ-123 and BQ-788, respectively, Sigma) will be perfused via intradermal microdialysis fibers while measuring skin blood flow (SkBF) at rest and during local heating. The antagonists will be dissolved in lactated Ringers solution and filtered using syringe microfilters (Whatman Puradisc 13 mm Syringe Filters, Florham Park, NJ). Following recovery from the microdialysis fiber placement, we will measure resting SkBF using laser Doppler flowmetry (LDF) for 15 min at all sites with the local heating devices off. Laser Doppler probes (MoorLAB, Temperature Monitor SH02, Moor Instruments, Devon, UK) which both measure and control local skin temperature, will be placed on the surface of the skin on the dorsal forearm over the microdialysis site. The laser Doppler probes will be maintained at 33°C during baseline and ET receptor antagonist infusion. Microdialysis fibers will then be perfused at 5.0 μ l/min for 45 minutes with the following drugs: the first fiber will be perfused with lactated Ringers; the second fiber will be perfused with 500 nM of the ET-A receptor antagonist (BQ-123)¹; the third fiber will be perfused with 300 nM of ET-B receptor antagonist (BQ-788)¹; the fourth fiber will be perfused with combined ET-A and ET-B receptor subtype antagonists (i.e. BQ-123 and BQ-788; 500 and 300 nM respectively). After perfusing the blocking agents, all four local heating devices will be raised until the skin temperature under the LDF probes reaches a stable temperature of 42°C². The SkBF response will be measured at each microdialysis site until a stable plateau is reached after heating. The microdialysis perfusions of antagonists will continue throughout the local heating response to maintain ET-A and ET-B receptor inhibition. Each series of perfusions will be followed by a perfusion of sodium nitroprusside (SNP, 28 mM) through the microdialysis fiber combined with local heating to 43°C to determine maximal SkBF. Cutaneous vascular conductance (CVC) will be calculated as mean SkBF/mean arterial pressure. We will collect blood samples for the measurement of estradiol, progesterone, testosterone, and endothelin-1 at the end of the recovery period just prior to beginning the perfusions, and again prior to maximal heating.

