Visit 4: Blood Vessel Assessment 2: The fifth visit is will occur 14 days after beginning losartan. This visit is approximately 5 hours long, and is identical to Visit 2 (Blood Vessel Assessment 1).

Visit 5: VO₂max Testing. This visit will last ~1 hour. Participants will be fasted from alcohol and caffeine for 12 hours, food for 4 hours, and exercise for 24 hours prior to testing. Exercise tests will be conducted in the stress testing laboratory in the NMPCC and overseen by a Certified Exercise Physiologist and Nurse Practitioner after clearance from the study physician, [name]. A resting 12-lead ECG and blood pressure will be taken in the supine and standing position. If resting BP is $\geq 200/110$ mmHg, the test will not be performed. A standard ramp treadmill protocol will be used, consisting of 1.5-minute stages where the speed and grade is increased incrementally. Expired gases will be collected and analyzed using the Parvo Medics Metabolic Cart. Exercise BP, HR, and ECG will be taken throughout, along with ratings of perceived exertion. This is a symptom-limited metabolic stress test; test termination criteria are based on ACSM guidelines (RER ≥ 1.10 , plateau in HR or VO₂ despite increased workload), and absolute indications for test termination such as chest pain, ECG abnormalities or arrhythmias, BP $>250/115$ mmHg, or participants request to stop. [name] will review the exercise test results. The NMPCC will send the test results to be read and interpreted by their cardiologist, [name]. In the event of a positive test or if additional follow up is needed, the NMPCC will contact the participant's primary care doctor.

Procedures in Normotensive Women (4 visits):

Visit 1: Screening/orientation: The first visit is about 1 hour long and includes

- 1). Completion of informed consent, medical history, and menstrual cycle history
- 2). Measures of height and weight,
- 3). Measures of resting blood pressure and 12-lead electrocardiogram
- 4). Blood Draw

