Sample size estimates were calculated for our main outcome variables in Specific Aim 1 based on previously published data in normotensive and pre-hypertensive adults utilizing arterial infusions of the ET-1 receptor antagonist. A three level 2x2 General Linear Mixed Model will be used to compare normotensive and hypertensive PMW on the outcomes. The hierarchical structure is needed as sites are nested within measurements, which are nested within individuals. The model assumptions of linearity and normality, will be evaluated using Box-Cox and Shapiro-Wilk tests, respectively. Outliers and influential cases will be screened for and removed. The covariance structure will be chosen using nested model comparisons. Violations of the assumptions will be remedied using transformations suggested by the Box-Cox test. *Post-hoc* comparisons will have the Bonferroni adjustment applied. The alpha is set at 0.05 for each analysis, and will be adjusted by the number of primary dependent variables to control for multiple comparisons. In order to find a large effect ($\rho\eta^2 = 0.50$), a sample of size of 38 women is required to achieve a power greater than 0.8. In order to account for screen failures, subject attrition and potential microdialysis fiber failure, we will recruit 60 women (30 normotensive and 30 hypertensive).

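### The Aim 1 model is justified by a purely nested hierarchy, but perfusate is crossed with visit; without a woman-by-perfusate term, one residual can mis-test pooled group-by-antagonist and losartan-by-antagonist contrasts

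*Combined protocol and SAP*

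**What the plan says.** The Statistical Plan, first paragraph, states: "A three level 2x2 General Linear Mixed Model will be used to compare normotensive and hypertensive PMW on the outcomes". Group is the only factor it names; neither visit nor perfusate appears as a fixed effect. The reason given for three levels is "The hierarchical structure is needed as sites are nested within measurements, which are nested within individuals". On covariance it says only "The covariance structure will be chosen using nested model comparisons", without listing the structures to be compared.

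Section 6 (Procedures) describes the data. Each assessment uses "Four microdialysis fibers (Bioanalytical Systems) with a membrane length of 10mm", with a fixed set of contents: "the first fiber will be perfused with lactated Ringers", the second and third carry BQ-123 and BQ-788, and "the fourth fiber will be perfused with combined ET-A and ET-B receptor subtype antagonists". The second assessment (Visit 4 for women with high BP, Visit 3 for normotensive women) "is identical to Visit 2 (Blood Vessel Assessment 1"). Only the women with high BP take losartan between the two assessments.

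**The concern.** A hierarchy of woman, visit within woman and site within visit has no place for a woman's own lasting response to a particular antagonist. If she has one, her BQ-123 readings at the two visits are correlated beyond her general level of skin blood flow. The nested model puts that shared part into site noise. Two tests then go wrong in opposite directions:

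- A group-by-antagonist contrast averaged over both visits treats the two visits as independent replicates, so its standard error is too small.
- The losartan-by-antagonist contrast (group by visit by perfusate) is a difference between visits, in which the lasting response cancels. It is still judged against an error that contains that response, so its standard error is too large.

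The second test matters most here. The study's stated aim is how angiotensin II and endothelin-1 interact, and this contrast addresses that question directly.

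**Working it through.** **Inputs from the documents.** 38 women (Statistical Plan), taken as two equal groups; 2 assessments; 4 perfusates; alpha 0.05. The plan will divide alpha by a number of primary variables that it does not state, so 0.05 is used here.

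**Assumed.** 'Measurements' means visits. Site variance is ve, woman-by-perfusate variance is vp, and θ = vp/ve. The documents give no value for θ; 0.25, 0.5 and 1 are shown as a range.

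**The plan's own figure.** The 38 women are stated as required for a partial eta squared of 0.50. At alpha 0.05, the F-test set-ups tried needed 4 to 16 women, so the figure does not reproduce. That is a separate matter; 38 is used below only as the analysed size.

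**Step 1: error each contrast needs.** Take the model y = woman + visit within woman + woman-by-perfusate + residual, with balanced data.

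- Group-by-perfusate averaged over visits: error ve + 2vp, on 3 × (38 − 2) = 108 df.
- Group-by-visit-by-perfusate: error ve, on 108 df.
- The plain nested model pools the two: [(ve + 2vp) + ve]/2 = ve + vp, on 216 df.

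One residual cannot serve both tests unless vp = 0.

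**Step 2: ratio of reported to true standard error.**

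- Group-by-antagonist, pooled over visits: √[(1 + θ)/(1 + 2θ)]
- Losartan-by-antagonist: √(1 + θ)

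**Step 3: size and power for 1-df tests.** With Φ the standard normal distribution function:

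- Size, group-by-antagonist: 2Φ(−1.96 × √[(1 + θ)/(1 + 2θ)])
- Size, losartan-by-antagonist: 2Φ(−1.96 × √(1 + θ))
- Power, losartan-by-antagonist, where a correct analysis has 80%: Φ(2.80 − 1.96 × √(1 + θ))

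Example at θ = 0.5. The first ratio is √(1.5/2) = 0.866, so size is 2Φ(−1.697) = 0.09. The second is √1.5 = 1.225, so size is 2Φ(−2.401) = 0.016 and power is Φ(2.80 − 2.401) = Φ(0.399) = 0.655.

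| θ | SE ratio, group-by-antagonist | Size, 1 df | Size, 3 df (simulated) | SE ratio, losartan-by-antagonist | Size, 1 df | Power (80% if correct) |
|---|---|---|---|---|---|---|
| 0 | 1.00 | 0.05 | 0.05 | 1.00 | 0.05 | 80% |
| 0.25 | 0.91 | 0.07 | 0.09 | 1.12 | 0.03 | 73% |
| 0.5 | 0.87 | 0.09 | 0.12 | 1.22 | 0.02 | 66% |
| 1 | 0.82 | 0.11 | 0.16 | 1.41 | 0.01 | 51% |

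Simulation of the balanced design agrees with the 1-df columns. A REML fit to one simulated data set (200 women, vp = ve = 0.5) gave a nested residual of 1.03, where the two contrasts need 1.5 and 0.5. Adding the woman-by-perfusate term recovered a residual of 0.51 and a component of 0.52.

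**Step 4: what is not affected.** At a single visit each woman gives one reading per perfusate, so a baseline group-by-antagonist contrast needs vp + ve, which is what the nested residual estimates. Its simulated size was 0.047 to 0.053. The group and group-by-visit terms average over perfusates and kept size 0.047 to 0.052.

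**Step 5: if the crossed term is a candidate.** An F test of woman-by-perfusate (108 and 108 df) detects it with probability 0.67, 0.97 and 1.00 at θ = 0.25, 0.5 and 1. Keeping the term only when p < 0.05, the 1-df group-by-antagonist size is 0.055, 0.049 and 0.050, and losartan-by-antagonist power is 79%, 80% and 80%.

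**The case against.** The strongest reply is that the plan has its own safeguard, the choice of covariance by nested model comparisons. Step 5 shows that this works if the woman-by-perfusate term is among the structures compared. At θ of 0.5 or more the term is almost never missed. At 0.25 it is missed about a third of the time, but size and power still come back to within about a point. A reader might infer that data-based selection cannot repair the problem; the figures do not support that. What survives is narrower: no candidates are listed, and a hierarchy described as purely nested invites comparisons such as dropping the visit level, which never bring in the crossed term.

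Second, the quoted sentence is literally true of the physical sites. That stands, but the contrasts of interest are between perfusates, and those labels recur at both visits.

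Third, the plan names no perfusate factor. If the 2x2 is group by visit alone, there is no antagonist contrast to distort. That also stands: the point applies to perfusate contrasts, which the four-fiber design exists to provide, and not to every possible set of fixed terms.

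Fourth, averaging a group comparison over visits mixes group with losartan, so baseline is the natural place to compare groups, and there the nested model is sound. This limits the type I error concern but leaves the losartan-by-antagonist loss untouched.

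**Conclusion.** The concern holds conditionally. It rests on three assumptions: that measurements are visits, that perfusate contrasts are analysed, and that vp is above zero with no crossed term fitted. Persistent differences between women in antagonist response are plausible, but the documents do not quantify them, and at vp = 0 there is no distortion.

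Under those assumptions, and for θ between 0.25 and 1, the pooled group-by-antagonist contrast has a true 1-df type I error of about 0.07 to 0.11. The losartan-by-antagonist standard error is overstated by 12% to 41%, which costs about 7 to 29 points of power from 80%.

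A reader might infer that every comparison of normotensive and hypertensive women rejects too often, or that the errors are certain to be wrong. Neither follows: baseline contrasts keep their size, and the distortion depends on an unreported variance. The change is still worth making, because the plan as worded does not lead the analyst to the term that gives its central interaction the right error.

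**What to change.** In the first paragraph of the Statistical Plan:

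- Name group, visit and perfusate as fixed factors, with their interactions.
- State that perfusate is crossed with visit within woman.
- Prespecify random effects for woman, visit within woman and woman-by-perfusate, or an equivalent covariance over the 2 × 4 = 8 visit-perfusate cells.
- Use Kenward-Roger degrees of freedom.
- Reserve nested model comparisons for structure beyond this.

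The cost is SAP wording and one extra variance component, with no new data, procedure or participant. Error degrees of freedom for the perfusate contrasts fall from 216 to about 108 at 38 women, a small loss. If the component is estimated as zero, the result is essentially that of the nested model. With the term included, simulated size was about 0.05 for both tests at every value tried.

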A Mixed Design ANOVA will be used to evaluate if losartan administration alters endothelial ET-1 protein expression ETB receptor expression on endothelial cells, along with ETA and ETB receptor expression on vascular smooth muscle cells in hypertensive PMW compared to that of normotensive PMW. Since values are expressed as ratios, if the assumptions of the Mixed Design ANOVA are not satisfied a Generalized Linear Mixed Model will be used. In order to find a moderately small effect ($\rho\eta^2 = .09$), a sample of size of 38 is required to achieve a power greater than 0.8. The model also assumes of linearity, sphericity, and normality, which will be evaluated using Box-Cox, Mauchly's, and Shapiro-Wilk tests, respectively. Outliers and influential cases will be screened for and removed. *Post-hoc* comparisons will have the Bonferroni adjustment applied. The alpha is set at 0.05 for each analysis, and will be adjusted by the number of primary dependent variables to control for multiple comparisons. Although we are planning on matching our groups based on age, body composition, VO_2max , and time since menopause, these may be potential covariates will be compared between groups using t-tests for continuous data and tests for χ^2 tests for categorical data. If a covariate is significantly different between groups it will be included in the analysis.

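### Both analyses remove outliers and influential cases with no technical cause required and no all-data analysis, so whether the planned alpha holds depends on a rule the plan does not state

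*Combined protocol and SAP*

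**What the plan says.** In the Combined protocol and SAP, Statistical Plan, the first paragraph (three-level mixed model) and the second paragraph (Mixed Design ANOVA of protein expression) contain the same sentence: "Outliers and influential cases will be screened for and removed". Removal is directed, not offered as an option. Neither paragraph names a diagnostic, a cut-off, the unit deleted or a required technical cause, and neither keeps an all-data analysis. No other section supplies these.

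The unit matters because, in the first analysis, "sites are nested within measurements, which are nested within individuals". A site value, a visit or a whole woman could be deleted.

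Each paragraph also plans a remedy that keeps the data. In the first, "Violations of the assumptions will be remedied using transformations suggested by the Box-Cox test". In the second, "if the assumptions of the Mixed Design ANOVA are not satisfied a Generalized Linear Mixed Model will be used". Neither says whether the remedy comes before or after removal.

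The plan means to control error. Alpha is 0.05 per analysis and "will be adjusted by the number of primary dependent variables to control for multiple comparisons".

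**The concern.** In both paragraphs the sentence follows directly on the assumption tests, and influence is a property of a fitted model. The natural reading is that values leave the analysis because they fit badly, not because a measurement failed. If values are removed for lying far from the fitted group means, the error variance shrinks, yet the test treats what remains as a complete sample. The test can then reject too often.

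With the cut-off, unit and order open, they could also be settled after results are seen, and no all-data result would show what that choice did. The adjustment of alpha for several primary variables gives no protection against this.

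**Working it through.** **Inputs from the documents.** Alpha 0.05 before adjustment; 38 women required (19 v 19 if equal) and 60 recruited (30 v 30); two groups, two visits.

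**Assumed, because the documents are silent.** The rule and cut-off; one pass of removal; a two-sided test; normal data; within-woman correlation 0.5 and 0.8.

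**Reduction to a simple test.** With one value per woman per visit, the group-by-visit test is a two-sample t-test on change (visit 2 − visit 1). The group test is a two-sample t-test on the woman's mean. Null datasets were simulated (60,000 or more per setting), the rule was applied, and the t-test was run on what remained.

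**The plan's own figure first.** With all data kept, the error rate is 4.9–5.1%, so the planned 5% is reproduced.

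**What each influence rule means.** For residual e, pooled SD s, n women per group, h = 1/n and two fitted means, Cook's D = (e/s)² × h / [2(1 − h)²].
- D > 4/38 with n = 19: |e|/s > √[(4/38) × 2 × (18/19)² × 19] = 1.9.
- D > 4/60 with n = 30: |e|/s > √[(4/60) × 2 × (29/30)² × 30] = 1.9.
- D > 1: |e|/s > √[2 × (18/19)² × 19] = 5.8, or √[2 × (29/30)² × 30] = 7.5.

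So Cook's above 4/n is slightly stricter than 2 SD, and Cook's above 1 removes almost nothing.

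**Error rates (%), nominal 5%, range over both sizes**

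| Rule | Women screened on the tested quantity | Visit values screened within group: group-by-visit test | Visit values screened within group: group test |
|---|---|---|---|
| All data | 4.9–5.1 | 4.9–5.1 | 4.9–5.1 |
| Cook's > 1 | no rise | no rise | no rise |
| 3 SD | 5.4–5.6 | 5.1–5.2 | up to 5.7 |
| 2 SD | 10.2–10.6 | 6.0–7.5 | 11.6–13.1 (with Cook's > 4/n) |
| Cook's > 4/n | 11.1–11.4 | 6.2–8.0 | see row above |

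- **Other rules with no inflation.** Pooled 2 SD screening that ignores group gives 5.0–5.2%. Screening women on their mean and testing change, or the reverse, gives 4.8–5.1% at every cut-off tried.
- **Sensitivity to definition.** A cut-off of 3 on studentised residuals, instead of 3 SD, gives 5.9–6.2% when women are screened on the tested quantity.
- **Site values.** A three-level model, 19 v 19, three assumed variance sets: all data 4.3–6.0%; 2 SD on within-visit residuals 4.5–5.5%; 2 SD on marginal residuals 7.9–11.6%.

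**Several outcomes.** The second paragraph lists "endothelial ET-1 protein expression ETB receptor expression on endothelial cells, along with ETA and ETB receptor expression on vascular smooth muscle cells", which is four outcomes. Suppose all four are primary and independent, each tested at 0.05/4 = 0.0125. With visit-value screening, the chance of at least one false positive on the group-by-visit test is about 7–10%. By 1 − (1 − p)⁴, this corresponds to p of about 1.8–2.6% per test instead of 1.25%.

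**Holding alpha is not enough.** Pooled group-blind 2 SD screening shrinks a true 0.8 SD difference to about 0.67. It cuts power from 67% to 57% (19 v 19) or from 86% to 77% (30 v 30).

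**Order of steps.** With lognormal data (assumed log SD 0.4 and 0.7), a 3 SD rule removes 0.4–1.1 women per dataset on the raw scale but at most 0.03 after Box-Cox. Transforming first does not rescue a 2 SD rule: the error is 10.5–10.9% that way and 6.5–7.9% with removal first.

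**The case against.** The strongest reply is that the plan states no rule, so no error rate belongs to it. That stands. Several rules cause no inflation, and a 3 SD rule adds at most about 0.7 points with normal data.

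A reader might infer that the error of each test roughly doubles. That needs a strict cut-off applied to the very quantity tested, or, for the group effect, to visit values within group. The second paragraph asks whether losartan alters expression compared with normotensive women, which is the group-by-visit test. With visit-value screening, that test reaches only about 6–8%.

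A reader might also infer a chance of 10–16% of at least one false positive across the four expression outcomes. On the group-by-visit test, that needs all four to be primary, a 2 SD or Cook's 4/n rule, and screening on the tested quantity. The documents support none of these. The first paragraph ties the main outcomes to Specific Aim 1, and the procedures describe staining of vein-wall cells only for ET-1 and ET-B receptors.

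It could be said that only technical failures were meant. The plan does name one: "In order to account for screen failures, subject attrition and potential microdialysis fiber failure, we will recruit 60 women". But there it justifies the recruitment target and is not a condition for exclusion. The procedures say that "The SkBF response will be measured at each microdialysis site until a stable plateau is reached after heating", and give no criterion for a failed fiber. If technical failure was intended, the proposed wording costs nothing.

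Loss of numbers is not the problem. The margin is 60 − 38 = 22 women, and a 2 SD rule on the tested quantity removes on average 1.4 of 38 or 2.5 of 60.

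**Conclusion.** The point holds as a conditional one. Both analyses direct removal with no technical cause and no all-data result. Depending on the rule later chosen, the error at nominal 5% runs from no inflation, through about 6–8% (group-by-visit test, visit values screened by 2 SD or Cook's > 4/n), to about 10–11% (women screened on the tested quantity) or 12–13% (group effect, visit values screened). Rules that hold alpha by ignoring group can still shrink a true effect and cost power.

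These figures rest on assumed rules, normal data and one-pass removal. The Generalized Linear Mixed Model planned for ratio data was not simulated. The documents do not support a claim that this trial will exceed its alpha, or by how much. They do show that its control depends on a choice left open. This should be changed; confidence in the gap is high, and in its size medium.

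**What to change.** In both paragraphs of the Statistical Plan, replace the removal sentence with:

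> The primary analysis keeps all valid observations. An observation is excluded only for a technical failure (first paragraph: for example failure of a microdialysis fiber; second paragraph: failure of cell collection or staining) documented when it occurs and before outcome results are analysed. Assumption violations are handled first by the planned remedy (first paragraph: Box-Cox transformation; second paragraph: Generalized Linear Mixed Model). An analysis without influential cases is reported only as a sensitivity analysis, with its diagnostic, cut-off and unit deleted fixed before the data are analysed (for example, women with Cook's distance above 4/n).

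The cost is a few sentences, one extra sensitivity run, and somewhat wider intervals when extreme but valid values occur. With normal data, keeping all observations holds the planned 5%.

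### Replacing Bonferroni with Holm's step-down rule, for the primary outcomes and the post-hoc contrasts, would recover some power at no cost in family-wise error; the present rule is valid

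*Combined protocol and SAP*

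**What the plan says.** The Statistical Plan has two paragraphs, one for the Specific Aim 1 mixed model and one for the protein-expression ANOVA. Each applies the same two rules.

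- Post-hoc level: "comparisons will have the Bonferroni adjustment applied". The method is named; the contrasts are not listed.
- Outcome level: "The alpha is set at 0.05 for each analysis, and will be adjusted by the number of primary dependent variables". No method is named and no number of variables is given.

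The first paragraph implies more than one primary outcome: "Sample size estimates were calculated for our main outcome variables in Specific Aim 1". The second names ET-1 and ETB in endothelial cells, "along with ETA and ETB receptor expression on vascular smooth muscle cells in hypertensive PMW compared to that of normotensive PMW", which makes four. Each paragraph arrives at 38 women for power above 0.8, at a partial eta squared of 0.50 in the first ("a sample of size of 38 women is required to achieve a power greater than 0.8") and 0.09 in the second ("a sample of size of 38 is required to achieve a power greater than 0.8"). Neither says whether the 38 was found at 0.05 or at the adjusted alpha. No step-down or other sequential rule appears.

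**The concern.** Fixed Bonferroni holds every test to 0.05/k, even after some hypotheses in the family have been rejected. Holm relaxes the threshold after each rejection and keeps the same family-wise guarantee without any assumption about how the outcomes are related. In a study sized at 38 women with several outcomes, a rule that is never less powerful deserves consideration. What is at stake is the chance of showing the second and later effects in a family. The validity of a positive finding is not in question.

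**Working it through.** **Inputs.** From the Statistical Plan: alpha 0.05, N = 38, partial eta squared 0.50 and 0.09. The outcome rule is read as 0.05/k. k is not stated: it is at least 2 in the first paragraph and four by listing in the second. The endothelial-cell procedure describes staining only for ET-1 and ET-B, so 2 to 4 is a fair range for the expression analysis. Assumed: 80% power per outcome at unadjusted two-sided 0.05, and correlation 0 to 0.5 between outcomes.

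**The plan's own 38.** With f² = η²/(1−η²) and F on 1 and 36 df:

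- η² = 0.50: f² = 1.00, and λ = f²N = 38. Power is 0.9997 even at 0.05/4 = 0.0125. The variants tried need about 6 to 20 women, so 38 is sufficient but is not the required number.
- η² = 0.09: f² = 0.09/0.91 = 0.0989. For a group-by-time interaction, λ = f² × 38 × 2/(1−ρ), with ρ the within-woman correlation (not stated). At alpha 0.05, 38 is reached at ρ = 0.10 (λ = 8.35, power 0.803). At alpha 0.0125 it is reached at ρ = 0.40 (λ = 12.53, power 0.812). The figure is therefore reproducible only with inputs that the plan does not give.

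**The two rules.** Bonferroni rejects when p ≤ 0.05/k. Holm orders the p-values and rejects the j-th smallest if, for every i up to j, the i-th smallest is at most 0.05/(k−i+1). The first threshold is the same under both rules, so the chance of at least one rejection is identical. Later thresholds are larger under Holm.

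**Hand check, k = 2, both real, correlation 0.** The mean z is 1.960 + 0.842 = 2.80.

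- Bonferroni, per outcome: Φ(2.80 − 2.241) = 0.712. Both shown: 0.712² = 0.51.
- Holm, per outcome: 0.712 + (0.80 − 0.712) × 0.712 = 0.775. Both shown: 0.80² − 0.088² = 0.63.

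At correlation 0.5 the simulated per-outcome gain is 0.052, giving 0.712 + 0.052 = 0.764.

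**Simulation, correlation 0 to 0.5.**

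| Case | Per outcome, Bonferroni | Per outcome, Holm | All shown, Bonferroni | All shown, Holm |
|---|---|---|---|---|
| k = 2, both real | 0.71 | about 0.77 | 0.51–0.57 | 0.63–0.68 |
| k = 4, all real | 0.62 | 0.71–0.73 | 0.15–0.31 | 0.38–0.53 |
| k = 4, two real | 0.62 | 0.64–0.65 | – | – |
| k = 4, one real | 0.62 | 0.62 | – | – |

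The lower all-shown values belong to correlation 0 and the higher to 0.5. The per-outcome Holm values run the other way. With two of four real, Holm's family-wise error is 0.036 to 0.039, below 0.05.

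**Small-sample version.** With t tests on 36 df, k = 4 and all real, power per outcome is 0.60 against 0.70 to 0.72. The sample needed for 80% mean power under Holm, relative to Bonferroni, is 0.79 to 0.82 with all four real, about 0.95 with two real and 0.998 with one real.

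**Effect of correlation on Holm's gain.** At correlation 0, 0.5 and 0.8, with all effects real:

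- k = 4, per outcome: 0.107, 0.090, 0.077.
- k = 4, all four shown: 0.236, 0.213, 0.184.
- k = 2, per outcome: 0.062, 0.052, 0.044.

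The gain falls as correlation rises.

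**The case against.** The strongest reply is that nothing here is wrong. Bonferroni is prespecified and protects the error rate, and it has matching simultaneous confidence intervals, which Holm lacks in simple form. That stands. It limits the point to an optional gain in efficiency and means that the change has a cost.

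The headline figures also take the most favourable case, in which every outcome in the family is truly affected, and they start from 80% power at unadjusted 0.05, which the documents do not establish. That stands too, which is why the two-of-four and one-of-four cases are shown.

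A reader might infer three stronger things that the documents do not support:

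- That power is scarce throughout. At the first paragraph's own effect size, 38 women give power near 1.00 after adjustment, so Holm returns essentially nothing for those main tests.
- That outcomes moving together would enlarge the gain. The documents give no correlation, and the calculation shows the opposite. The skin blood flow and expression outcomes also belong to separate analyses, each with its own alpha of 0.05.
- That the plan states a division by k. It says only that alpha is adjusted by the number of variables; 0.05/k is the likely reading.

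What survives is that, for the same error guarantee, Holm rejects everything Bonferroni rejects and sometimes more.

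**Conclusion.** A cheap improvement, not an error. Where several effects in a family are real, Holm adds about 0.05 to 0.06 to per-outcome power with two outcomes and 0.09 to 0.11 with four, under the assumptions stated. With two of four real it adds 0.02 to 0.03, and with one almost nothing. It does not raise the chance of at least one positive result. The benefit falls mainly on the expression outcomes, where power at 0.09 has no evident slack, and on the post-hoc contrasts. The gain for this trial cannot be fixed, because k, the contrasts, the correlations and the alpha behind 38 are not stated.

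**What to change.** In each of the two analyses, list the primary dependent variables and the post-hoc contrasts. Then replace the alpha/k rule and the Bonferroni adjustment with Holm's procedure at family-wise 0.05 within each listed family, before the data are analysed. Report 95% confidence intervals and label them as unadjusted. State as well which alpha lies behind the 38.

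The cost is wording in the Statistical Plan; no additional women or measurements are needed. The downside is that Holm has no simple matching simultaneous intervals, so an unadjusted interval may exclude no effect where the adjusted test does not reject. The report should say that decisions follow the adjusted tests.
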